**Table 2-1      Overview of analyses on some safety endpoints**

Analysis period	AEs & SAEs	AEs by severity	Study drug related AEs	AEs-SMQ	Risk	Notables for (vitals/ECG), lab criteria
Day 1 – Week 8	crude incidence					
Day 1 – Week 16	crude incidence	crude incidence	crude incidence	crude incidence	crude incidence	crude incidence
Entire Treatment	crude incidence	crude incidence	crude incidence	exposure time	crude incidence	crude incidence
	exposure time			adjusted incidence	exposure time	
	adjusted incidence*				adjusted incidence	

\*Exposure-adjusted incidence rates will be done for the following :

at the PSOC for AE and SAE and Level 1 for Risks and SMQ analyses

at the PT level for common AEs, which is defined as at least 2% of the patients in the combined AIN457 groups during the initial treatment period (i.e. up to week 24) or events that had an incidence rate of at least 5.0 cases per 100 subject-years in the combined AIN457 groups during the entire treatment period

## 2.8.2      Laboratory data

The summary of lab data will only include on treatment data, which are defined as those lab assessments after the first dose of study treatment and on or before last dose + 84 days.

The summary of laboratory evaluations will be presented for three groups of laboratory tests (hematology, chemistry and urinalysis). In addition to the individual laboratory parameters the ratios “total cholesterol / HDL” and “apolipoprotein B / apolipoprotein A1” will be derived and summarized.

For urinalysis, frequency tables will be presented.

Descriptive summary statistics for the change from baseline to each study visit will be presented. These descriptive summaries will be presented by laboratory test and treatment

group. Change from baseline will only be summarized for subjects with both baseline and post baseline values and will be calculated as:

$$\text{change from baseline} = \text{post baseline value} - \text{baseline value}$$

For each parameter, the maximum change (maximum decrease and maximum increase) from baseline, will be analyzed analogously.

In addition, shift tables will be provided for all parameters to compare a subject's baseline laboratory evaluation relative to the visit's observed value. For the shift tables, the normal laboratory ranges will be used to evaluate whether a particular laboratory test value was normal, low, or high for each visit value relative to whether or not the baseline value was normal, low, or high. If appropriate, the shifts to the most extreme laboratory test value within a treatment phase (either initial up to week 24 or entire) will be presented as well (including category "high and low"). These summaries will be presented by laboratory test and treatment group.

The following laboratory parameters will be analyzed with respect to numerical Common Terminology Criteria for Adverse Events (CTCAE) grades, given in [Table 2-2](#): hemoglobin, platelets, white blood cell count, neutrophils, lymphocytes, creatinine, total bilirubin (TBL), gamma-glutamyl transferase (GGT), alanine aminotransferase (ALT), aspartate aminotransferase (AST), alkaline phosphatase (ALP), glucose, cholesterol, triglycerides (TG).

These summaries will be split into hematology and chemistry.

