## **2 Statistical methods**

### **2.1 Data analysis general information**

Summary statistics for continuous variables include N, mean, standard deviation, minimum, lower quartile, median, upper quartile, and maximum. For binary or discrete variables the absolute number of subjects in each category and relative frequencies will be provided.

Unless otherwise specified, p-values will be presented as 2-sided p-values and the type I error rate (alpha) will be 5%.

Inferential efficacy comparisons with placebo will generally focus on the first 16-weeks of treatment except for radiographic assessment which will focus on the first 24-weeks of treatment unless otherwise specified.

Efficacy and safety data for the placebo-controlled period (or the entire treatment period as appropriate) will be presented by randomized treatment groups. Subjects may be included in more than one treatment group for some analyses (e.g. exposure-adjusted AEs over the entire treatment period).

Note that the treatment groups for a subject may differ depending on the time period of the analysis and whether one assesses the subject for efficacy or safety (see [Section 2.2.2](#) for details).

Data may also be presented by a combination of the 'original' and 'switch' treatment groups. These treatment groups represent the treatment combinations the subjects experience over the course of the entire trial.

Subjects will receive treatment at BSL, Weeks 1, 2 and 3, followed by treatment every 4 weeks starting with Week 4 through Week 104 (with last dose at Week 100).

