## **2.8 Safety analyses**

Summaries may be performed separately for initial (Week 1-16) period and entire treatment period (including follow-up). Week 16 is chosen due to the fact that placebo patients may be rescued as early as week 16. Use of data up to and including the last visit before rescue provides an unbiased comparison between AIN and placebo; data collected beyond week 16 are included in analyses which summarize the entire treatment period.

Safety analyses will be performed on treatment received (or actual treatment) as described below:

The actual treatment or treatment received for summaries of safety data will differ to the treatment assigned at randomization only if a subject received the wrong treatment during the entire study.

For those subjects who received not the treatment randomized, i.e. who received erroneously the wrong treatment at least once, an additional AE listing will be prepared displaying which events occurred after the treatment errors.

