**Table 2-2 CTCAE grades for laboratory parameters to be analyzed**

CTCAE v4.0 Term	Grade 1	Grade 2	Grade 3	Grade 4
HGB decreased (Anemia)	<LLN - 100 g/L	<100 - 80 g/L	<80 g/L	
Platelet count decreased	<LLN - 75.0 x10e9 /L	<75.0 - 50.0 x10e9 /L	<50.0 - 25.0 x10e9 /L	<25.0 x 10e9 /L
White blood cell decreased	<LLN - 3.0 x 10e9 /L	<3.0 - 2.0 x 10e9 /L	<2.0 - 1.0 x 10e9 /L	<1.0 x 10e9 /L
Neutrophil count decreased	<LLN - 1.5 x 10e9 /L	<1.5 - 1.0 x 10e9 /L	<1.0 - 0.5 x 10e9 /L	<0.5 x 10e9 /L
Lymphocyte count decreased	<LLN - 0.8 x 10e9/L	<0.8 - 0.5 x 10e9 /L	<0.5 - 0.2 x 10e9 /L	<0.2 x 10e9 /L
Creatinine increased*	>1 - 1.5 x baseline; >ULN - 1.5 x ULN	>1.5 - 3.0 x baseline; >3.0 x ULN	>3.0 baseline; >6.0 x ULN	
TBL increased	>ULN - 1.5 x ULN	>1.5 - 3.0 x ULN	>3.0 - 10.0 x ULN	>10.0 x ULN
GGT increased	>ULN - 2.5 x ULN	>2.5 - 5.0 x ULN	>5.0 - 20.0 x ULN	>20.0 x ULN
ALT increased	>ULN - 3.0 x ULN	>3.0 - 5.0 x ULN	>5.0 - 20.0 x ULN	>20.0 x ULN
AST increased	>ULN - 3.0 x ULN	>3.0 - 5.0 x ULN	>5.0 - 20.0 x ULN	>20.0 x ULN
ALP increased	>ULN - 2.5 x ULN	>2.5 - 5.0 x ULN	>5.0 - 20.0 x ULN	>20.0 x ULN
Glucose increased (Hyperglycemia )	>ULN - 8.9 mmol/L	>8.9 - 13.9 mmol/L	>13.9 - 27.8 mmol/L	>27.8 mmol/L

CTCAE v4.0 Term	Grade 1	Grade 2	Grade 3	Grade 4
Glucose decreased (Hypoglycemia)	<LLN - 3.0 mmol/L >ULN - 7.75 mmol/L	<3.0 - 2.2 mmol/L >7.75 - 10.34 mmol/L	<2.2 - 1.7 mmol/L >10.34 - 12.92 mmol/L	<1.7 mmol/L >12.92 mmol/L
Cholesterol high	mmol/L	mmol/L	mmol/L	mmol/L
Hypertriglyceride mia	1.71 - 3.42 mmol/L	>3.42 - 5.7mmol/L	>5.7 - 11.4 mmol/L	>11.4 mmol/L

\*Note: for "creatinine increased" the baseline criteria do not apply

Shift tables will be presented comparing baseline laboratory result (CTCAE grade) with the worst results (expressed in CTCAE grade) during the treatment phase (either initial up to week 24 or entire) analyzed. Of note, baseline will be defined as last assessment prior to first dosing in initial treatment phase.

Subjects with abnormal laboratory values will be listed and values outside the normal ranges will be flagged.

Summaries for newly occurring or worsening clinically notable lipid abnormalities will also be provided cumulatively for each of the following parameters and categories:

- HDL:
  - <=LLN
  - <0.8 x LLN
- LDL, cholesterol, triglycerides:
  - >=ULN
  - >1.5 x ULN
  - >2.5 x ULN

Newly occurring or worsening liver enzyme abnormalities will also be summarized based on the event criteria given in [Table 2-3](#):

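### The SAP ends the initial safety period at Week 16 because placebo subjects may then switch, but defines the initial phase of its worst-value laboratory shift tables as running to Week 24 with no cut at the switch

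*SAP*

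**What the plan says.** SAP 2.8 sets an initial safety period of Weeks 1-16 alongside the entire treatment period. It gives the reason: "Week 16 is chosen due to the fact that placebo patients may be rescued as early as week 16". It adds: "Use of data up to and including the last visit before rescue provides an unbiased comparison between AIN and placebo". Data after Week 16 go to the entire-period summaries. The rows of Table 2-1 agree: Day 1 to Week 8, Day 1 to Week 16, and entire treatment. There is no Week 24 row.

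SAP 2.8.2 uses a different boundary in two places:

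- Normal-range shifts to the worst value, to be shown if appropriate: "the shifts to the most extreme laboratory test value within a treatment phase (either initial up to week 24 or entire").
- CTCAE shifts from baseline to the worst grade, below Table 2-2: "during the treatment phase (either initial up to week 24 or entire) analyzed".

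The laboratory values eligible for these tables are "those lab assessments after the first dose of study treatment and on or before last dose + 84 days". That window does not end at the switch. On grouping, SAP 2.1 states: "Efficacy and safety data for the placebo-controlled period (or the entire treatment period as appropriate) will be presented by randomized treatment groups". SAP 2.5.3 puts the end of the placebo-controlled period at Week 24. SAP 2.2.2 also allows summaries by treatment sequence.

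**The concern.** The SAP gives a sound reason for stopping at Week 16 and then does not apply it to the laboratory tables most sensitive to it. A worst-value table keeps one value per subject, so a single post-switch result is enough to change a subject's category.

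The active columns gain the same two visits, so the longer window is not itself the bias. The problem is that, for switched placebo subjects, the added values reflect secukinumab. A real drug effect on a laboratory parameter, in either direction, would look smaller than it is. Neutrophils are among the graded parameters, and Protocol 3.6 reports slightly more mild neutropenia on secukinumab than on placebo. The entire-period tables cannot restore the comparison, because by then the remaining placebo subjects have switched too.

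**Working it through.** **Which values are affected**

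- Protocol 6.5 has blood drawn before dosing, so the Week 16 draw of a switching subject is still on placebo. The Week 20 draw follows one secukinumab dose, and the Week 24 draw follows two.
- Placebo responders start secukinumab at Week 24, after that visit's draw, and contribute no post-switch value.

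**Share of placebo subjects who switch at Week 16**

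Inputs: about 66% expected non-responders (Protocol Amendment 1 rationale, item 4); 330 placebo subjects (Protocol 9.7; check: 990 × 3/9 = 330); 25% dropout in the first year (Protocol section 4).

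- No dropout adjustment: 0.66 × 330 = 218 subjects.
- Assumption: dropout accrues evenly and 66% applies to those remaining. Lost by Week 24: 0.25 × 24/52 = 11.5%. Share: 0.66 × 0.885 = 58.4%, or 193 subjects.
- Extreme case, all 25% lost before Week 16: 0.66 × 0.75 = 49.5%, or 163 subjects.

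**Share of placebo-column draws that are post-switch**

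Table 6-1 is broken in the extracted text, so the visit counts are a reading of it.

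- Hematology and chemistry, if drawn at Weeks 1, 2, 3, 4, 8, 12, 16, 20 and 24: 2 of 9 draws follow the switch. 0.584 × 2/9 = 13.0%; 0.66 × 2/9 = 14.7%.
- With even dropout applied to both numerator and denominator: 0.66 × (0.904 + 0.885) / (9 − 0.25 × 90/52) = 1.180/8.567 = 13.8%, inside that range. Here 90 is the sum of the nine visit weeks.
- Lipids, if drawn at Weeks 8, 16 and 24: 1 of 3 follows the switch. 0.584/3 = 19.5%; 0.66/3 = 22%.
- In a placebo non-responder sequence column, subjects with all draws have 2/9 = 22% post-switch (lipids 1/3).

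**Why no attenuation figure follows**

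The documents give no incidence of laboratory abnormalities. Three sets of assumptions for hematology and chemistry show how far the answer moves:

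- Per-draw risk 0.5% on placebo, odds ratio 2, immediate effect, independent draws. Any abnormal draw in nine: placebo 4.41%, active 8.61%, switched placebo subject (seven placebo and two secukinumab draws) 5.36%. Loss = share × (5.36 − 4.41)/(8.61 − 4.41), which is 13.2% at 58.4% switching and 14.9% at 66%.
- Risk per 4 weeks of 1% against 2%, immediate effect. The 24-week difference falls from 5.56 points to 4.47 (58% switching) or 4.31 (66%), a loss of 19.7% to 22.4%.
- Effect visible only at the Week 24 draw, so that one draw in nine counts: 0.584/9 = 6.5% to 0.66/9 = 7.3%.

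The loss runs from about 7% to about 22%, depending only on inputs the documents do not give.

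**The case against.** The strongest reply is that the SAP does not commit to a pooled placebo column run to Week 24. The normal-range version is conditional. The CTCAE version offers a choice of phase that an entire-period table alone could satisfy. SAP 2.2.2 allows treatment sequence, and SAP 2.1 says a subject's group may differ by analysis period. Elsewhere the SAP handles the switch with care: exposure is split at the switch (2.4.1), Table 4-3 attributes a post-switch event to the active dose, and Table 4-2 has before-and-after rules for by-visit laboratory summaries. This part stands: a reader might infer that on-secukinumab values will certainly be counted as placebo, and the documents do not support that as fact. But none of these rules governs the worst-value shifts, and display by sequence does not remove the mixing.

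A reader might also take the statement that treatment received "will differ to the treatment assigned at randomization only if a subject received the wrong treatment during the entire study" as fixing switched subjects under placebo. It does not: in context it concerns dosing errors, and the switch is part of the randomized sequence.

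Week 24 has a natural origin as the end of Treatment Period 1 and the first database lock. That explains the wording, but it does not answer the SAP's own reason for Week 16.

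The footnote to Table 2-1 also says "during the initial treatment period (i.e. up to week 24"). It sets a frequency threshold in the combined secukinumab groups, so it is a difference in terms and contaminates nothing.

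Other outputs limit the harm: the Day 1 to Week 16 notables, by-visit tables through Week 16, box plots over time for neutrophils, liver and lipid parameters, and listings by treatment sequence.

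**Conclusion.** The inconsistency is in the current SAP and the point holds, as minor. If an initial-phase worst-value table is produced as SAP 2.8.2 defines it, either the placebo column (by randomized group) or the placebo non-responder columns (by sequence) will contain values taken on secukinumab. By randomized group, these come from about 58-66% of placebo subjects and make up about 13-15% of hematology and chemistry draws. These figures rest on the 66% planning expectation, on even dropout for the lower end, and on the visit schedule as read from Table 6-1.

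The direction is towards dilution of any effect that appears within eight weeks of starting secukinumab. It is tempting to attach a definite percentage to that dilution, but the documents do not support one. No hypothesis test, error rate or power figure is involved.

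**What to change.** In both sentences of SAP 2.8.2 that define the initial phase (the normal-range worst-value shift and the CTCAE worst-grade shift), replace the Week 24 boundary with: *initial up to Week 16 (before the first secukinumab dose for placebo subjects)*. Because the Week 16 draw precedes dosing, this brings post-switch values in the placebo column to zero.

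The cost is a change to two sentences, and a randomized worst-value comparison that covers 16 weeks instead of 24. Later values remain in the entire-period tables. Keeping Week 24 and cutting only placebo non-responders at the switch would also remove the contamination, but it would give those subjects fewer draws in which to record an extreme value than subjects in the active columns.

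Aligning the Table 2-1 footnote is optional and serves consistency only. It removes no bias, and with a Week 16 window fewer preferred terms might reach the 2% threshold. The alternative threshold of 5.0 per 100 subject-years would be unaffected.

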**Table 2-2 CTCAE grades for laboratory parameters to be analyzed**

CTCAE v4.0 Term	Grade 1	Grade 2	Grade 3	Grade 4
HGB decreased (Anemia)	<LLN - 100 g/L	<100 - 80 g/L	<80 g/L	
Platelet count decreased	<LLN - 75.0 x10e9 /L	<75.0 - 50.0 x10e9 /L	<50.0 - 25.0 x10e9 /L	<25.0 x 10e9 /L
White blood cell decreased	<LLN - 3.0 x 10e9 /L	<3.0 - 2.0 x 10e9 /L	<2.0 - 1.0 x 10e9 /L	<1.0 x 10e9 /L
Neutrophil count decreased	<LLN - 1.5 x 10e9 /L	<1.5 - 1.0 x 10e9 /L	<1.0 - 0.5 x 10e9 /L	<0.5 x 10e9 /L
Lymphocyte count decreased	<LLN - 0.8 x 10e9/L	<0.8 - 0.5 x 10e9 /L	<0.5 - 0.2 x 10e9 /L	<0.2 x 10e9 /L
Creatinine increased*	>1 - 1.5 x baseline; >ULN - 1.5 x ULN	>1.5 - 3.0 x baseline; >3.0 x ULN	>3.0 baseline; >6.0 x ULN	
TBL increased	>ULN - 1.5 x ULN	>1.5 - 3.0 x ULN	>3.0 - 10.0 x ULN	>10.0 x ULN
GGT increased	>ULN - 2.5 x ULN	>2.5 - 5.0 x ULN	>5.0 - 20.0 x ULN	>20.0 x ULN
ALT increased	>ULN - 3.0 x ULN	>3.0 - 5.0 x ULN	>5.0 - 20.0 x ULN	>20.0 x ULN
AST increased	>ULN - 3.0 x ULN	>3.0 - 5.0 x ULN	>5.0 - 20.0 x ULN	>20.0 x ULN
ALP increased	>ULN - 2.5 x ULN	>2.5 - 5.0 x ULN	>5.0 - 20.0 x ULN	>20.0 x ULN
Glucose increased (Hyperglycemia )	>ULN - 8.9 mmol/L	>8.9 - 13.9 mmol/L	>13.9 - 27.8 mmol/L	>27.8 mmol/L

CTCAE v4.0 Term	Grade 1	Grade 2	Grade 3	Grade 4
Glucose decreased (Hypoglycemia)	<LLN - 3.0 mmol/L >ULN - 7.75 mmol/L	<3.0 - 2.2 mmol/L >7.75 - 10.34 mmol/L	<2.2 - 1.7 mmol/L >10.34 - 12.92 mmol/L	<1.7 mmol/L >12.92 mmol/L
Cholesterol high	mmol/L	mmol/L	mmol/L	mmol/L
Hypertriglyceride mia	1.71 - 3.42 mmol/L	>3.42 - 5.7mmol/L	>5.7 - 11.4 mmol/L	>11.4 mmol/L

\*Note: for "creatinine increased" the baseline criteria do not apply

Shift tables will be presented comparing baseline laboratory result (CTCAE grade) with the worst results (expressed in CTCAE grade) during the treatment phase (either initial up to week 24 or entire) analyzed. Of note, baseline will be defined as last assessment prior to first dosing in initial treatment phase.

Subjects with abnormal laboratory values will be listed and values outside the normal ranges will be flagged.

Summaries for newly occurring or worsening clinically notable lipid abnormalities will also be provided cumulatively for each of the following parameters and categories:

- HDL:
  - <=LLN
  - <0.8 x LLN
- LDL, cholesterol, triglycerides:
  - >=ULN
  - >1.5 x ULN
  - >2.5 x ULN

Newly occurring or worsening liver enzyme abnormalities will also be summarized based on the event criteria given in [Table 2-3](#):

**Table 2-3 Liver-related events**

Parameter	Criterion
ALT	>3xULN; >5xULN; >8xULN; >10xULN, >20xULN
AST	>3xULN; >5xULN; >8xULN >10xULN; >20xULN
ALT or AST	>3xULN; >5xULN; >8xULN >10xULN; >20xULN
TBL	>1.5xULN, >2xULN, >3xULN,
ALP	>2xULN, >3xULN. >5xULN
ALT or AST & TBL	ALT or AST>3xULN & TBL >2xULN; ALT or AST >5xULN & TBL >2xULN; ALT or AST >8xULN & TBL >2xULN; ALT or AST >10xULN & TBL >2xULN
ALP & TBL	ALP >3xULN & TBL >2xULN ALP >5xULN & TBL >2xULN
ALT or AST & TBL & ALP	ALT or AST>3xULN & TBL >2xULN & ALP <2xULN ( Hy's Law )

Parameter	Criterion
	
Note: elevated ALP may suggest obstruction as a consequence of gall bladder or bile duct disease; ALP may also be increased in malignancy. FDA therefore terms Hy's Law cases as indicators of pure hepatocellular injury. This does not mean that cases of ALT or AST >3xULN & TBL >2xULN & ALP <math>\geq</math>2xULN may not result in severe DILI.

Notes:

- 1) In studies which enroll subjects with pre-existing liver disease, baseline LFT may be increased above ULN; in such a case it is meaningful to add the condition "and worse than baseline" to the abnormality criteria

For a combined criterion to be fulfilled, all conditions have to be fulfilled on the same visit. The criteria are not mutually exclusive, e.g. a subject with ALT = 6.42xULN is counted for ALT >3xULN and ALT>5x ULN.

Individual subject data listings will be provided for subjects with abnormal laboratory data. Data of subjects with newly occurring or worsening liver enzyme abnormalities will be listed in an additional listing.

Box plots over time will be presented for selected laboratory parameters (neutrophils, liver and lipid parameters).

In addition, individual subject data listings will be provided for all parameters.

The laboratory values below Lower Level of Quantification (LLQ) or above Upper Level of Quantification (ULQ) will be imputed as LLQ or ULQ, respectively. The numerical part of the reported result will be treated as the actual LLQ or ULQ. These laboratory values will be displayed in listings using the standard unit with the reported sign ("<" or ">")."

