| 7. Sum row 6 for each column for PASI score | | | | |
| a. Divide body into four areas: head, arms, trunk to groin, and legs to top of buttocks. | | | | |
| b. Generate an average score for the erythema, thickness, and scale for each of the 4 areas (0=clear, 1-4=increasing severity). | | | | |
| c. Sum scores of erythema, thickness, and scale for each of the 4 area. | | | | |

[figure not shown]
- d. Generate a percentage for skin covered with psoriasis for each area and convert that to a 0-6 scale. ‡
- e. Multiply score of item c above times item d above for each area and multiply that by 0.1, 0.2, 0.3 and 0.4 for head, arms, trunk, and legs, respectively.
- f. Add these scores to get the PASI score.

† Erythema, thickness, and scale are measured on a 0-4 scale (none, slight, mild, moderate, severe)

‡ Area scoring criteria (score: % involvement).

- 0: 0% (clear)
- 1: <10%
- 2: 10-<30%
- 3: 30-<50%
- 4: 50-<70%
- 5: 70-<90%
- 6: 90-100%

Derived from [Feldman and Krueger, 2005](#). Psoriasis assessment tool in clinical trials. Ann Rheum Dis; 64;ii65-ii68.

19 Appendix 7: Liver event and Laboratory trigger Definitions and Follow-up Requirements

Table 19-1 Liver Event and Laboratory Trigger Definitions

| Definition/ threshold | |
|-----------------------|---|
| LIVER | 3 x ULN < ALT / AST \leq 5 x ULN |
| LABORATORY TRIGGERS | 1.5 x ULN < TBL \leq 2 x ULN |
| LIVER EVENTS | ALT or AST > 5 x ULN ALP > 2 x ULN (in the absence of known bone pathology) TBL > 2 x ULN (in the absence of known Gilbert syndrome) ALT or AST > 3 x ULN and INR > 1.5 Potential Hy's Law cases (defined as ALT or AST > 3 x ULN and TBL > 2 x ULN [mainly conjugated fraction] without notable increase in ALP to > 2 x ULN) Any clinical event of jaundice (or equivalent term) ALT or AST > 3 x ULN accompanied by (general) malaise, fatigue, abdominal pain, nausea, or vomiting, or rash with eosinophilia Any adverse event potentially indicative of a liver toxicity * |

* These events cover the following: hepatic failure, fibrosis and cirrhosis, and other liver damage-related conditions; non-infectious hepatitis; benign, malignant and unspecified liver neoplasms

TBL: total bilirubin; ULN: upper limit of normal

Table 19-2 Follow Up Requirements for Liver Events and Laboratory Triggers

| Criteria | Actions required | Follow-up monitoring |
|--------------------------------------|---|--|

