| > 1.5 to ≤ 2 × ULN (patient is asymptomatic) | Repeat LFT within the next week If elevation is confirmed, initiate close observation of the patient | Investigator discretion Monitor LFT within 1 to 4 weeks or at next visit |
| Jaundice | Discontinue the study drug immediately Hospitalize the patient Establish causality Complete liver eCRF | ALT, AST, TBL, Alb, PT/INR, ALP and γGT until resolution ^c (frequency at investigator discretion) |
| Any AE potentially indicative of a liver toxicity* | Consider study drug interruption or discontinuation Hospitalization if clinically appropriate Establish causality Complete liver eCRF | Investigator discretion |

* These events cover the following: hepatic failure, fibrosis and cirrhosis, and other liver damage-related conditions; non-infectious hepatitis; benign, malignant and unspecified liver neoplasms

TBL: total bilirubin; ULN: upper limit of normal

^a Elevated ALT/AST > 3 × ULN and TBL > 2 × ULN but without notable increase in ALP to > 2 × ULN

^b (General) malaise, fatigue, abdominal pain, nausea, or vomiting, or rash with eosinophilia

^c Resolution is defined as an outcome of one of the following: (1) return to baseline values, (2) stable values at three subsequent monitoring visits at least 2 weeks apart, (3) remain at elevated level after a maximum of 6 months, (4) liver transplantation, and (5) death.

20 Appendix 8: Clinically notable laboratory values

The following guidance will be used to define expanded limits and notable abnormalities of key laboratory outcomes.

Clinically notable values will be forwarded to Novartis in the same time as sent to the investigators. Any intervention based on these laboratory values should be discussed with Novartis personnel.

| Laboratory variable | Notable criteria |
|--|-------------------------------|
| Liver function and related variables | |
| SGOT (AST) | >3 x ULN |
| SGPT (ALT) | >3 x ULN |
| Bilirubin | >2 x ULN |
| Alkaline phosphatase | >2.5 x ULN |
| Renal function, metabolic and electrolyte variables | |
| Creatinine (serum) | >2 x ULN |
| Hematology variables | |
| Hemoglobin | 20 g/L decrease from Baseline |
| Platelet count | <100 x 10 ⁹ /L |
| White blood cell count | <0.8 x LLN |
| Neutrophils | <0.9 x LLN |

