Post-baseline safety	Summary visit information (e.g. lab, ECG, etc.)	
For visits without switch of treatment in the window, the measurement closest to the target will be used. In the event two measurements are taken equally apart (e.g. 1 before target date and 1 after) the first one will be used.
 
For visits during which the patient switches from placebo to AIN the following will be done based on whether or not the patient met the rescue criteria:
 

• If the analysis visit window is <= week 16(for non-responders) or week 24 (for responders), then:

• If available, the closest measurement to the target date which is ON or BEFORE the switch date will be used (i.e. the closest measurement to target which is on placebo).

• If there are no data on or before the switch then the closest measurement to the target date after the switch will be used.

• If the analysis visit window is > week 16(for non-responders) or week 24 (for responders), then

• If available, the closest measurement to the target date which is AFTER the switch date will be used (i.e. the closest measurement to target which is on AIN).

• If there are no data AFTER the switch then the closest measurement to the target date before the switch will be used.

Timing of measurement	Type of data	Rule
		Cases where the same parameter is recorded more than once on the same date will be handled as follows: 

• If time of completion exists the earliest measurement will be used;

• If time does not exist the measurement from the lowest CRF visit number will be used.

Post-baseline safety	Notable abnormalities (e.g. lab)	The most extreme measurement in the window will be used. Note this means a patient can have a notably high and notably low measurement within a window.

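### SAP Table 2-3 counts combined liver criteria, including Hy's Law, only when all parts are met at one undefined 'visit', so non-overlapping rises in one subject are left out of the combined rows

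*SAP*

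**What the plan says.** **SAP 2.8.2, Table 2-3.** Three kinds of combined row are planned: ALT or AST with total bilirubin (TBL), ALP with TBL, and the Hy's Law row, "ALT or AST>3xULN & TBL >2xULN & ALP <2xULN". A note below the table governs all of them: "For a combined criterion to be fulfilled, all conditions have to be fulfilled on the same visit". ALT, AST, ALT or AST, TBL and ALP also have rows of their own. The criteria overlap ("The criteria are not mutually exclusive"), and there is a dedicated listing: "Data of subjects with newly occurring or worsening liver enzyme abnormalities will be listed in an additional listing".

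**Protocol Appendix 7.** Table 19-1 reads "Potential Hy's Law cases (defined as ALT or AST > 3 x ULN and TBL > 2 x ULN", then adds that bilirubin should be mainly conjugated and that ALP should show no notable increase. A footnote to Table 19-2 repeats the thresholds: "Elevated ALT/AST > 3 × ULN and TBL > 2 × ULN but without notable increase in ALP to > 2 × ULN". Neither place says when the values must occur relative to each other.

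**SAP 4.1.1 and Tables 4-1 and 4-2.** Repeat and unscheduled samples are mapped to analysis windows like scheduled ones. For notable abnormalities such as laboratory values, "The most extreme measurement in the window will be used". The SAP does not say whether this applies to the combined rows of Table 2-3, nor whether 'visit' there means a sample date, a nominal visit or an analysis window.

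**The concern.** The SAP adds a condition to the protocol's definition without giving a reason. The protocol's own follow-up makes sequential samples likely: repeat liver tests within 48 hours or within the next week, then monitoring to resolution for most liver events (section 7.3 and Table 19-2). After Week 52, scheduled chemistry is 8 weeks apart, and 12 weeks apart from Week 92 to Week 104 (Table 6-2). The transaminase and bilirubin values that together make up one episode may therefore lie on different dates.

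The combined rows are read to see whether any case exists, so a change from one to zero matters. The separate ALT/AST and TBL rows cannot replace them, because they do not show that the same subject had both. No Data Monitoring Committee is planned (protocol 8.4). Because 'visit' is undefined, two programmers could also report different counts from the same data.

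**Working it through.** The plan gives no figure here to reproduce. The check has three steps.

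**1. The definitions side by side**

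| Element | Protocol Appendix 7 | SAP Table 2-3 |
|---|---|---|
| ALT or AST | > 3 x ULN | > 3 x ULN |
| TBL | > 2 x ULN, mainly conjugated | > 2 x ULN |
| ALP | no rise to > 2 x ULN | < 2 x ULN |
| Timing | not stated | all on the same visit |

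The timing row is the substantive difference. Two smaller ones are the conjugated-fraction qualifier, absent from the SAP, and an ALP of exactly 2 x ULN, which only the SAP excludes.

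**2. Hypothetical profiles (x ULN; an arrow separates two visits)**

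| Profile | ALT | TBL | ALP | SAP, visit by visit | Protocol thresholds, ignoring timing |
|---|---|---|---|---|---|
| A | 8 → 4 | 1 → 2.5 | 1 | counted | met |
| B | 8 → 2.5 | 1 → 2.5 | 1 | not counted | met |
| C | 8 | 2.5 | 1 | counted | met |

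A and B both have bilirubin rising after the transaminase peak. Only B is lost, because ALT is no longer above 3 x ULN when TBL qualifies.

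**3. What happens if 'visit' means the analysis window**

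The contents of Table 4-1 are not in the available text, so I derived the windows from its stated rule, assuming they follow the chemistry visits in protocol Tables 6-1 and 6-2. The upper limit is the target day plus the integer part of half the gap to the next target day. The lower limit is the previous upper limit plus 1, and the first window starts on Day 2.

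- Week 1: upper limit 8 + int(7/2) = 11, so Days 2-11, 10 days.
- Week 2: Days 12-18, 7 days. Week 3: Days 19-25, 7 days.
- Week 4: upper limit 29 + int(28/2) = 43, so Days 26-43, 18 days.
- Week 8: Days 44-71, 28 days. Weeks 12-48 are also 28 days each.
- Week 52: Days 352-393, 42 days. Weeks 60-84: 56 days each. Week 92: Days 618-687, 70 days.

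The SAP's own example, in which Day 46 is re-aligned to Week 8, agrees.

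Now take a subject like B, with TBL qualifying *d* days after ALT/AST and ALT/AST no longer qualifying by then. If the ALT/AST day is uniform over a window of length *L*, the chance that the two values fall in different windows is min(1, *d*/*L*). The documents give no lag, so *d* is an assumption, shown at two values.

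| Window | L (days) | d = 7 | d = 14 |
|---|---|---|---|
| Week 1 | 10 | 7/10 = 70% | 100% |
| Weeks 2-3 | 7 | 7/7 = 100% | 100% |
| Week 4 | 18 | 7/18 = 39% | 14/18 = 78% |
| Weeks 8-48 | 28 | 7/28 = 25% | 14/28 = 50% |
| Week 52 | 42 | 7/42 = 17% | 14/42 = 33% |
| Weeks 60-84 | 56 | 7/56 = 12.5% | 14/56 = 25% |
| Week 92 | 70 | 7/70 = 10% | 14/70 = 20% |

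The edges bear no relation to the event. ALT on Day 43 (Week 4) and TBL on Day 44 (Week 8) are one day apart and not linked. ALT on Day 44 and TBL on Day 71 are 27 days apart and are linked.

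If 'visit' means the sample date, every subject like B is left out, by construction.

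**The case against.** Most of the case for leaving the rule alone is sound as far as it goes.

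- **The rule is explicit, pre-specified and gives few false pairings.** This stands, and is why the same-visit count should stay. It is reproducible, however, only once 'visit' is defined.
- **The protocol is silent, not contradicted.** A reader might infer that the SAP departs from a protocol rule counting rises on different dates. There is no such rule: Appendix 7 joins the thresholds and gives no timing. The documents support only that the SAP adds a condition the protocol does not state. The repeat-test intervals are follow-up instructions, not counting rules.
- **Late bilirubin rises are not all lost.** A reader might infer that any bilirubin rise after the transaminase peak goes uncounted. Profile A shows otherwise.
- **Affected subjects are not hidden.** They remain in the single-parameter rows, the listings and the shift tables to worst CTCAE grade. TBL above 2 x ULN without known Gilbert syndrome is itself a protocol liver event. This limits the consequence, but leaves the reader to assemble the case from listings.
- **Table 2-3 is not the only liver information.** AE, SAE, SMQ and risk summaries are also planned. SAP 2.8.6 (compound-specific safety) is in the contents but its text is not available, so no claim can be made about what else it covers.
- **The lags and uniform timing are assumed, and nothing in the documents says bilirubin lags.** This stands. The percentages describe how windows behave, not how often cases occur.

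**Conclusion.** The point holds in a limited form. Read visit by visit, the combined rows omit a subject whose ALT/AST has fallen to 3 x ULN or below at every visit where TBL exceeds 2 x ULN. The window reading recovers some of these subjects, but which ones depends on arbitrary edges: at an assumed 7-day lag the proportion missed runs from 10% in the longest window to 100% in the 7-day windows. These figures are conditional on non-overlapping rises and uniform timing, and on windows inferred from the stated rule. The documents give no incidence, so the expected number of missed cases cannot be stated, and it may be zero.

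A reader might infer that the trial could report no serious liver injury when a case exists. The documents do not support that: only the combined rows are affected, and the component values are reported elsewhere. The table is descriptive. The point justifies a cheap improvement to the sensitivity and clarity of a safety table, and no more.

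**What to change.** In SAP 2.8.2, Table 2-3:

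1. State whether 'visit' means the sample date or the analysis window, and if the latter, whether the most-extreme-value rule of Table 4-2 applies.
2. Keep the same-visit count.
3. Beside it, add a row for each combined criterion that counts subjects whose TBL > 2 x ULN falls on the same day as, or within a prespecified interval after, the qualifying ALT/AST (or ALP) elevation. The sponsor should choose and justify the interval, since the documents point to none. Use all scheduled and unscheduled on-treatment samples.
4. State which ALP value applies to the Hy's Law row when samples from different dates are combined.

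The cost is SAP wording and programming on data already collected. The downside is a few more cases for medical review, some with unrelated bilirubin rises.
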